#### C. Care in the Home

Did any healthcare worker provide services to you in your home during the last 28 days (4 weeks)?	Yes	No	Number of days	Number of hours per day
Nurse				
Home health aide				
Hospice worker				
Other		

PFS	Progression-free Survival
PFS2	Progression-Free Survival on the Next Line of Therapy
PK	Pharmacokinetics
PP	Per Protocol
PR	Partial Response
PT	Preferred Term
QD	Once Daily
QOL	Quality of Life
SAP	Statistical Analysis Plan
SOC	System Organ Class
TEAE	Treatment Emergent Adverse Event
TKI	Tyrosine Kinase Inhibitor
TTP	Time to Progression
TTR	Time to Response
VAS	Visual Analogue Scale
WHO	World Health Organization

CONFIDENTIAL Page 6 of 29

1. INTRODUCTION

This Statistical Analysis Plan (SAP) describes the detailed methodology for summary and statistical analyses of data from clinical protocol DCC-2618-03-002 (INTRIGUE) based on Amendment 6 of the study protocol, dated 23 October 2020. This document may modify the plans outlined in the protocol and supersedes the previous versions of the SAP and the statistical sections of the protocol.

Populations for analysis, statistical methods, data handling rules, and formats for data presentation are described within this document. The statistical analyses and summary tabulations described in this SAP will provide the basis for the results sections of the Clinical Study Report (CSR) for this trial. Analysis plan of population pharmacokinetics (PK) and exposure-response analysis, pharmacodynamics data, and quality-of-life (QOL) data collected for exploratory objectives will be separately documented.

Any changes to the data analysis methods after the SAP is finalized will be described in the CSR.

2. OVERALL STUDY DESIGN AND OBJECTIVES

2.1. Study Objectives

2.1.1. Primary Objective

To assess the efficacy (progression-free survival [PFS]) of DCC-2618 (ripretinib) by independent radiologic review (IRR) in patients with advanced gastrointestinal stromal tumors (GIST) who have previously received first-line therapy with imatinib

2.1.2. Key Secondary Objectives

- To assess objective response rate (ORR) by independent radiologic review using modified RECIST (mRECIST) criteria
- To assess Overall Survival (OS)

2.1.3. Other Secondary Objectives

- To assess the quality-of-life (QOL) during treatment as measured by:
 - EORTC QLQ-C30
 - Dermatology Life Quality Index (DLQI)
 - GP5 question from the FACT-G (burden of side-effects)
 - EuroQol Visual Analogue Scale (EQ-VAS)
- To assess Time to Tumor Progression (TTP) by independent radiologic review
- To assess efficacy parameters including, disease control rate (DCR), PFS based on Investigator assessment, duration of response (DOR) and time to response (TTR)
- To assess efficacy based on Choi criteria by independent radiologic review

CONFIDENTIAL Page 7 of 29

- To assess the PK/PD relationship of ripretinib
- To compare the safety profile of ripretinib to the safety profile of sunitinib

2.1.4. Exploratory Objectives

- To assess QOL during treatment as measured by:
 - Memory and concentration items from the PRO-CTCAE library
 - EQ-5D-5L
- To assess PFS on next line therapy (PFS2) based on local assessments
- To evaluate potential biomarkers in blood or tumor tissue which might predict response to ripretinib
 - To understand potential resistance mechanisms to ripretinib in GIST
 - To characterize KIT and PDGFRA mutations at baseline and ripretinib-driven longitudinal mutant allele frequency changes in plasma.
- To assess healthcare utilization

2.2. Study Design and Study Procedures

2.2.1. Study Design

This is a 2-arm, randomized, open-label, international, multicenter study comparing the efficacy of ripretinib to sunitinib in GIST patients who progressed on or were intolerant to first-line anticancer treatment with imatinib.

Approximately 426 patients will be randomized in a 1	:1 ratio to ripretinib 150 mg once daily
(QD) or sunitinib 50 mg QD, 4 weeks on, 2 weeks off	(6 weeks cycle).

Randomization will be stratified by:

- Mutational Status: KIT exon 9 mutation; KIT exon 11 mutation; KIT/PDGFRA WT; or other KIT (absence of exon 9 or 11)/PDGFRA mutations
 - Note: if a patient has a KIT exon 11 mutation, along with mutation(s)
 - o in KIT exon 9 and/or PDGFRA, the patient will be randomized as having a KIT exon 11 mutation, unless the mutation allele frequency (MAF) data is available then the mutation with the higher MAF will be used to categorize the patient for the purposes of randomization;
 - o in KIT other exon, the patient will be randomized as having a KIT exon 11 mutation.
- Intolerance to imatinib (Yes or No)

The primary endpoint for the study will be evaluated using the mRECIST Version 1.1 - GIST specific based on IRR.

Upon disease progression by mRECIST based on IRR, patients will discontinue their assigned treatment.

CONFIDENTIAL Page 8 of 29

2.2.2. Treatments and Assignment to Treatments

Approximately 426 patients (213 randomized to ripretinib and 213 randomized to sunitinib) will be randomized in this study at approximately 125 centers globally. Patients will be randomized to receive 150 mg QD of ripretinib or 50 mg of sunitinib in repeated 42-day cycles. Ripretinib will be given continuously and sunitinib will be given continuously for 4 weeks with a 2 week break. Sunitinib dose modifications are allowed per approved package insert or institutional guidelines.

Patients will be treated until they develop progressive disease based on IRR as per mRECIST, experience unacceptable toxicity, or withdraw consent. If the Investigator wishes to end treatment due to local progression based on mRECIST, without confirmation of progression by IRR, or before the independent read results are available, the Investigator must reach out to the Sponsor Medical Monitor to discuss.

Patients will be eligible to receive study drug for up to 2 years. This will be extended by agreement between the Sponsor and Investigator for patients who exhibit evidence of clinical benefit and tolerability to the drug, and who adhere to the study procedures. The study will end following the last patient last visit.

2.3. Determination of Sample Size

The sample size selection of 426 patients (n=213 ripretinib, n=213 sunitinib) was based on considerations for powering of the primary endpoint, secondary endpoints, detection of rare safety events and overall exposure to ripretinib. Patients will be randomized in a 1:1 ratio of ripretinib versus sunitinib.

Under the assumptions that median progression-free survival (mPFS) is 9 months for ripretinib and 6 months for sunitinib, the HR is about 0.667 for All Patients (AP) PFS (ripretinib vs sunitinib). A total of 262 events will be required to achieve a statistical power of 90% to test the hypothesis of no difference between ripretinib and sunitinib in AP. Accrual of 426 patients (213 in ripretinib and 213 in sunitinib) within 21 months is expected to have 262 PFS events occurred after additional 8 months of follow up. This has accounted for 20% of dropout rate (discontinuation without progressive disease per IRR or death).

It is further assumed that the mPFS is 9 months for patients with a KIT Exon 11 primary mutation (Ex11) in ripretinib and 5 months for KIT Ex11 in sunitinib, the HR is 0.556 for the KIT Ex011 PFS. A minimum of 151 PFS events in KIT Ex11 population have at least 95% power to test the hypothesis of no difference between ripretinib and sunitinib in KIT Ex11 population.

No interim analysis is planned for PFS based on IRR. The final analysis of PFS based on IRR will be performed in the Ex11 ITT population and in the AP ITT population (as defined in Section 4) using the same data cutoff, following the hierarchical testing sequence specified in Section 8.5. This final analysis is planned to occur when at least 151 PFS events in Ex11 ITT population and approximately 262 PFS events in AP ITT population have occurred. The analysis of PFS in Ex11 ITT population and AP ITT population will be based on the actual number of events observed in Ex11 ITT population and AP ITT population, respectively, at the time of final analysis of PFS.

CONFIDENTIAL Page 9 of 29

At the time of final analysis of PFS by IRR, ORR by IRR and OS in Ex11 ITT and AP ITT will be tested hierarchically as specified in Section 8.5. If all the testing preceding OS are statistically significant, OS in Ex11 ITT will be tested at 2-sided 0.05 significance level; if OS in Ex11 ITT is statistically significant, OS in AP ITT will be tested at 2-sided 0.05 significance level.

Assuming median OS is 40 months for sunitinib arm and 53.3 months for ripretinib arm (HR=0.75), 145 events in the Ex11 ITT population will have 40% power to detect the difference in OS between the two arms in the Ex11 ITT population with 2-sided significance level 0.05, and 200 events in the AP ITT population will have 52% power to detect the difference in OS between the two arms in the AP ITT population with 2-sided significance level 0.05.

There are two interim analyses (IA) of OS planned, both for early stopping for efficacy only, in each of the Ex11 ITT population and in the AP ITT population, respectively. The first IA for OS in each of the two populations will be performed at the same time as the final analysis for PFS based on IRR in the population. The second IA for OS will be performed with the data cutoff date approximately one year after the first IA. The final analysis of OS will be performed using the same data cutoff in both populations when at least 145 OS events in the Ex11 ITT population and approximately 200 OS events in the AP ITT population are observed. The overall two-sided nominal significance level for the efficacy analysis of OS will be preserved at 0.05. Formal efficacy boundary will be determined based on Lan-DeMets (O'Brien-Fleming) alpha spending function. Table 1 summarizes the operating characteristics and efficacy boundaries for the OS analyses based on projected number of OS events. The final analysis of OS in Ex11 ITT population and AP ITT population will be based on the actual number of events observed in Ex11 ITT population and AP ITT population, respectively, at the time of final analysis of OS. The exact boundary at each analysis will be calculated on the actual number of events at the time of data cutoff.

Table 1: Planned Stopping Boundaries for Overall Survival at Interim Analyses and Final Analysis

Analysis Population	Analysis	Number of Events (Info. Fraction)	Cumulative Alpha Spent	Efficacy Boundary p-value
	First IA	63 (44%)	0.001	0.001
Ex 11 ITT	Second IA	122 (84%)	0.029	0.029
	FA	145 (100%)	0.05	0.041
	First IA	88 (44%)	0.001	0.001
AP ITT	Second IA	169 (85%)	0.030	0.029
	FA	200 (100%)	0.05	0.041

Abbreviations: IA=interim analysis; FA=final analysis; ITT=intent-to-treat

The cumulative alpha spent and boundaries were calculated using software nQuery (version 8.7).

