8.2.2. Overall Survival

OS is defined as the time interval between the date of randomization and date of death from any cause. Patients who are still alive or are lost to follow-up will be censored at the date of last contact.

OS (months) = [date of death or censoring - date of randomization + 1]/30.4375

Analysis for OS in AP ITT Population will be stratified by the randomization stratification factors per IRT (mutation status [KIT exon 9 vs. KIT exon 11 vs. KIT/PDGFRA WT vs. other KIT {absence of exon 9 or 11}/PDGFRA] and intolerance to imatinib [yes vs. no]). Analysis for OS in Ex11 ITT population will be stratified by intolerance to imatinib per IRT [yes vs. no]. The p-value will be from a 2-sided stratified Log-rank test at 0.05 significance level for evaluation of treatment difference. Point estimate of hazard ratio will be obtained from a Cox proportional-hazards regression model stratified by randomization stratification factors per IRT; the associated 95% CI will be obtained using Wald method. OS will be summarized via KM methodology using the 25th, 50th (median), and 75th percentiles and survival probability at prespecified timepoints, each with associated 2-sided 95% confidence intervals. The estimated survival functions will be displayed in a KM plot.

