8.5. Multiple Comparisons/Multiplicity

To control familywise type-I error at 0.05 level, the hypothesis tests for treatment difference will be performed according to the hierarchical testing sequence below:

- 1. PFS by IRR in Ex11 ITT (two-sided 0.05 level)
- 2. PFS by IRR in AP ITT (two-sided 0.05 level)
- 3. ORR by IRR in Ex11 ITT (two-sided 0.05 level)
- 4. ORR by IRR in AP ITT (two-sided 0.05 level)
- 5. OS in Ex11 ITT (two-sided 0.05 level)

CONFIDENTIAL Page 22 of 29

6. OS in AP ITT (two-sided 0.05 level)

The testing starts from PFS in Ex11 ITT and each subsequent endpoint will only be tested if all the testing preceding to it have been statistically significant. If the testing for any endpoint fails to meet statistical significance, the testing and p-value for all the subsequent endpoints will be nominal and statistical significance won't be claimed for all the subsequent endpoints.

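### SAP 2.3 sets two significance levels for the same OS look: two-sided 0.05 in the text, about 0.001 in Table 1

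*SAP*

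**What the plan says.** SAP Section 2.3 first deals with the final analysis of PFS by independent review. At that time ORR and OS are to be tested in hierarchical order, and the OS rule is: "If all the testing preceding OS are statistically significant, OS in Ex11 ITT will be tested at 2-sided 0.05 significance level". The rule for all patients follows: "if OS in Ex11 ITT is statistically significant, OS in AP ITT will be tested at 2-sided 0.05 significance level".

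Further on, the same section plans two OS interims for efficacy plus a final OS analysis, and fixes the timing of the first: "The first IA for OS in each of the two populations will be performed at the same time as the final analysis for PFS". It then sets the error control. On the level it says: "The overall two-sided nominal significance level for the efficacy analysis of OS will be preserved at 0.05". The method named for the boundary is Lan-DeMets spending of the O'Brien-Fleming type. On the individual looks it adds: "The exact boundary at each analysis will be calculated on the actual number of events at the time of data cutoff".

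Table 1 gives boundary p-values of 0.001, 0.029 and 0.041 for the three looks in each population. The event counts are 63, 122 and 145 in Ex11 ITT and 88, 169 and 200 in AP ITT.

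Elsewhere in the SAP, Section 8.2.2 says of OS: "The p-value will be from a 2-sided stratified Log-rank test at 0.05 significance level for evaluation of treatment difference". Section 8.5 lists both OS steps of the sequence at two-sided 0.05. Neither mentions the boundary. Section 8.7 refers back to Section 2.3 for the OS interims.

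**The concern.** The PFS final analysis and the first OS interim are the same look, and Section 2.3 gives that look two thresholds that differ by a factor of 34 to 50 (0.05 against 0.00145 or 0.00135 unrounded, or 0.001 as printed). An OS p-value of, say, 0.02 at that look would be a confirmatory result under one paragraph and not under the other. In Ex11 it would also decide whether the AP test opens.

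OS is a key secondary endpoint inside the alpha-controlled sequence of an open-label trial. If the choice between the two paragraphs is made after the data are seen, the familywise control promised in Section 8.5 is no longer prespecified. If the 0.05 sentence is followed at the first look and Table 1 afterwards, OS does not keep its 0.05 level.

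**Working it through.** **Inputs (SAP 2.3 and Table 1).** OS looks at 63/122/145 events (Ex11) and 88/169/200 events (AP); overall two-sided level 0.05; Lan-DeMets O'Brien-Fleming spending; HR 0.75; 1:1 allocation; stated power 40% (Ex11) and 52% (AP).

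**Step 1: reproduce Table 1.** With 0.025 spent per side, the cumulative two-sided alpha at information fraction t is 4 × [1 − Φ(z₀.₉₈₇₅/√t)], where z₀.₉₈₇₅ = 2.2414.

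- Ex11, t = 63/145 = 0.4345: 4 × [1 − Φ(3.400)] = 0.00135.
- AP, t = 88/200 = 0.44: 4 × [1 − Φ(3.379)] = 0.00145.

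At the first look the boundary p-value equals the alpha spent. The later boundaries come from recursive numerical integration of the log-rank score process, with information = events/4.

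| | Cumulative alpha | Boundary p | Table 1 boundary p |
|---|---|---|---|
| Ex11 | 0.00135 / 0.0291 / 0.05 | 0.00135 / 0.0286 / 0.0415 | 0.001 / 0.029 / 0.041 |
| AP | 0.00145 / 0.0295 / 0.05 | 0.00145 / 0.0290 / 0.0414 | 0.001 / 0.029 / 0.041 |

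All values agree with Table 1 to within 0.001. The first-look boundaries are z = 3.21 (Ex11) and z = 3.18 (AP).

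**Step 2: which design does the stated power fit?** Power of a single test at 0.05 is Φ(|ln 0.75| × √D / 2 − 1.96).

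- D = 145: Φ(1.732 − 1.96) = 41.0%.
- D = 200: Φ(2.034 − 1.96) = 53.0%.
- Three-look design with the boundaries above: 40.1% and 51.9%.

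The SAP's 40% and 52% match the three-look design. The gap to a single test is only about 1 point, so this supports the boundary reading without proving it.

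**Step 3: type I error by rule.** First-crossing probabilities under no difference, each population alone:

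| Rule | Ex11 | AP |
|---|---|---|
| Spending boundaries at all three looks | 0.0500 | 0.0500 |
| 0.05 at look 1, then spending boundaries | 0.05000 + 0.01648 + 0.01717 = 0.0837 | 0.05000 + 0.01665 + 0.01680 = 0.0834 |
| 0.05 at look 1, then the printed 0.029 and 0.041 | 0.0834 | 0.0832 |

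**Step 4: what differs at the first look.** The observed HR needed is exp(−2z/√D).

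- Ex11, 63 events: 0.610 at z = 1.96; 0.446 at z = 3.21.
- AP, 88 events: 0.658 at z = 1.96; 0.507 at z = 3.18.

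An observed HR of about 0.45 to 0.61 (Ex11) or 0.51 to 0.66 (AP) therefore meets the 0.05 criterion and not the boundary.

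If the true HR is 0.75, the mean of the test statistic at this look is 0.2877 × √63 / 2 = 1.142 (Ex11) and 0.2877 × √88 / 2 = 1.349 (AP). The chance of meeting each criterion in favor of ripretinib is:

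- Ex11: 20.7% at 0.05, 1.9% at the boundary.
- AP, ignoring the Ex11 gate: 27.1% at 0.05, 3.3% at the boundary.
- Both populations, as the sequence requires for an AP claim: 16.5% at 0.05, 1.2% at the boundaries. This assumes HR 0.75 in both and correlation √(63/88) = 0.846.

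**The case against.** The best defense is that 0.05 means the total alpha allotted to OS. The interim text comes later in the same section, names this look as the first interim, preserves 0.05 overall, prints the 0.001 row and requires a boundary at each analysis. The SAP also states OS power at a two-sided level of 0.05, where the figures fit the three-look design, so the same phrase can denote the overall level. On this view only a cross-reference is missing, and Sections 8.2.2 and 8.5 are correct as lists of levels per hypothesis. The 8.4% and 8.3% also belong to a hybrid rule that no passage prescribes, and they arise only after four earlier tests have succeeded.

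Much of this stands. The overall-level reading is very likely the intent, it is a fair reading of Section 8.5 taken alone, and the design itself is sound. The inflated figures measure the consequence of the faulty sentence, not the intended design. The AP first-look figure of 27% is a marginal probability; with the Ex11 gate it is about 16.5%.

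The defense does not rescue the sentence. It does not call 0.05 an overall level. It attaches 0.05 to the test done at the PFS final analysis and makes AP testing depend on the Ex11 result there. Section 8.7 only sends the reader back to the section that contains the conflict. The protocol cannot settle it either: its Section 9.5 plans no interim analyses, and SAP Section 1 says the SAP supersedes the protocol's statistical sections.

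**Conclusion.** The concern holds. Section 2.3 states a decision rule for a confirmatory OS test that contradicts its own group-sequential design: 0.05 against about 0.001 at the same look. The Table 1 design is internally consistent and holds OS at 5.0% in each population. Using 0.05 at the first look and Table 1 afterwards would give about 8.4% (Ex11) and 8.3% (AP).

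These figures assume the projected event counts and the usual large-sample log-rank approximation. They take each OS test on its own once the earlier steps in the sequence have been passed. The contradiction itself rests only on the text. It must be fixed because it concerns the criterion for a claim and should be settled before OS data are seen.

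**What to change.** In Sections 2.3, 8.2.2 and 8.5, state that two-sided 0.05 is the overall OS level in each population. State also that every OS look, including the one at the PFS final analysis, is judged against the Lan-DeMets O'Brien-Fleming boundary recalculated from the actual events, with Table 1 giving the planned values.

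As an optional clarification, Section 8.5 could add that failing to cross an interim OS boundary is not a failed test in the hierarchy, so OS can still be tested at the later looks.

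The cost is SAP wording only: sample size, event targets, timing and Table 1 stay as they are. An OS claim at the first look becomes harder than the present sentence says, as Table 1 already intends.

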3. GENERAL ANALYSIS CONVENTIONS

3.1. Study Periods

The study will include screening, treatment, safety follow up (30 days post last dose of study treatment), and overall survival follow-up periods.

CONFIDENTIAL Page 10 of 29

3.2. Study Visits

All study assessments will be performed according to the schedule of assessments in the protocol. In general, for by-visit summaries, data recorded at nominal visits will be presented. Unscheduled visits will be mapped to a scheduled visit if possible, using a window based on all the available actual visit dates for the scheduled visits.

3.3. Study Day

Reference start date will be defined as Cycle 1 Day 1. Study Day will be calculated from the reference start date and used to show start/stop day of the assessments and events as follows,

- For assessments/events on/after the reference start date, Study Day=(date of assessment/event reference start date) +1
- For assessments/events before the reference start date, Study Day=(date of assessment/event reference start date)

3.4. Baseline

Unless specified otherwise, baseline measurements will be the most recent (i.e., last non-missing) value prior to receiving the first dose of study medication.

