Molecular pathology report with identified KIT/PDGFRA mutation status 	X										
████████████████████	█										
Optional Tumor Biopsy 									X		
Radiologic Imaging 	X				X		X		X		
████████████████████		█					█		█		

CT=computed tomography; ECG=electrocardiogram; ECOG= Eastern Cooperative Oncology Group; EOT=End of treatment; EORTC QLQ-C30=European Organisation for Research and Treatment of Cancer Quality of Life Questionnaire for Cancer 30-item; EQ-5D-5L= EuroQol 5-Dimension 5-Level; DLQI= Dermatology Life Quality Index; MRI=magnetic resonance imaging, MUGA=multigated acquisition; PD=pharmacodynamic; PK=pharmacokinetic; PS=performance status

1. All assessments must be performed predose and within the visit specified windows, unless otherwise described. Additional unscheduled safety or efficacy assessments may be performed at any time as clinically indicated to determine the relevance of specific findings and/or the duration of events.
2. Screening must occur within 28 days prior to the first dose of study drug.
3. All patients will be followed until withdrawal of consent or death from any cause. After the Safety Follow-Up Visit, patients will be contacted every 3 months (±1 month) to collect long-term survival data including OS and PFS2 (i.e. next line of therapy, start date of next line of therapy, date of progression on the next line of therapy).
4. Any medication or non-drug therapy taken, or procedure performed within 30 days prior to screening and before the first dose of study drug.
5. A serum pregnancy test will be performed for females of child-bearing potential by a central laboratory at screening. Urine pregnancy tests will be performed at all subsequent Day 1 visits of each cycle and the EOT visit. Local serum pregnancy test may be performed instead of urine, if it is the standard practice of the site and results are received prior to the patient being dosed in the clinic.
6. Randomization may occur on Day -1. Patients scheduled for Cycle 1 Day 1 on Monday may be randomized on the preceding Friday.

7. Patients taking anticoagulants will also have a test at Cycle 1 Day 15. Monitoring of coagulation tests must be increased for as long as deemed clinically appropriate following a change in anticoagulant dose during the study.

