15. The EORTC QLQ-C30, EQ-5D-5L, DLQI, GP5 question from FACT-G, and PRO-CTCAE Questions 46 and 47 must be performed before the patient is evaluated by the Investigator or designee on the day of the scheduled visit. If the dermatologic examination or imaging assessments are completed within 7 days of the scheduled visit and the patient is not evaluated by the Investigator or designee, the questionnaires do not need to be completed on that day. The GP5 question from FACT-G will be completed first followed by EORTC-QLQ-C30, DLQI, EQ-5D-5L and PRO-CTCAE Questions 46 and 47. The questionnaires will be collected via an electronic patient reported outcome system. Patients will complete all questionnaires at home on Day 29 of Cycle 3 and beyond via the electronic patient report outcome system. Patient-entered data will not be modified by the Investigator or site staff, ePRO vendor, CRO or Sponsor.
16. On days of study visits, patients will be informed to take the study drug at the study site after predose assessments are completed. See Section 5.3 for dosing and administration details.
17. For DCC-2618 patients only, PK sampling will be performed at the following time points: Cycle 1 Day 1 pre-dose and 6 hours after dosing, Cycle 1 Day 15 pre-dose, and 2 and 6 hours after dosing, pre-dose at Day 1 of Cycles 2, 3 and Day 1 of every other cycle thereafter (e.g. Cycle 5, 7, 9, etc.), and at the EOT Visit. All pre-dose samples must be collected within 60 minutes before dosing and all post-dose samples must be collected  $\pm 30$  minutes of the nominal time point. An unscheduled PK sample may be taken at the time of onset of a new, suspected, treatment-related adverse event when requested by the Sponsor.
18. **South Korea Only:** Pharmacogenomics samples will not be collected.
19. Molecular pathology report with mutational status of KIT/PDGFR $\alpha$  must be available. Mutation status must be identified using a tissue based PCR/sequencing assay. Molecular pathology report with mutation status of KIT/PDGFR $\alpha$  must be provided to the Sponsor for review prior to randomization. If the molecular pathology report is not available or insufficient, an archival tumor tissue sample or fresh biopsy is required for mutation status confirmation at the central laboratory prior to randomization. Specific instructions will be provided in the Study Reference Manual.

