### **5.11. Blinding and Unblinding**

This is an open-label study.

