## **9.8. Statistical Methods**

### **9.8.1. General Methods**

Data collected in this study will be documented using summary tables and patient data listings. Continuous variables will be summarized using descriptive statistics (number of patients, mean, median, standard deviation, minimum, and maximum). Categorical variables will be summarized using frequencies and proportions. Time-to-event data will be summarized via Kaplan-Meier (KM) methodology using the 25th, 50th (median), and 75th percentiles with associated 2-sided 95% confidence intervals.

Unless specified otherwise, baseline measurements must be the most recent value prior to receiving the first dose of study medication. If an assessment is not available, then the last assessment prior to that visit would be used.

Medical history, AEs, and concurrent procedures will be coded using Medical Dictionary for Regulatory Activities (MedDRA). Prior and concomitant medications will be coded using the World Health Organization Drug Dictionary.

Unless specified, the ITT population is used for efficacy analysis and the safety population is used for the safety analysis. The primary and secondary efficacy endpoints will be analyzed for both the Ex 1 1 ITT and the AP ITT populations.

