8.3.3.4. EQ-VAS

EQ-VAS is the sixth item of EQ-5D-5L. It records the patient's self-rated health on a vertical visual analogue scale with endpoints labeled "the best health you can imagine" and "the worst health you can imagine." A patient is asked to "mark an X on the scale to indicate how your health is TODAY" and "write the number you marked on the scale in the box below."

EQ-VAS at each post-baseline time point, and the last on-treatment assessment, and change in scores from baseline will be summarized using descriptive statistics. The change in EQ-VAS from baseline at specific timepoints (3 and 6 months) will be compared between the two arms. The EQ-VAS at 3 months will be calculated as the average of its score on C2D29 visit and C3D1 visit; similarly, the EQ-VAS at 6 months will be calculated as the average of its score on C5D29 visit and C6D1 visit.

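### Quality-of-life baseline is tied to the first dose, not to randomisation, so in this open-label trial some baseline scores, EQ-VAS above all, may be recorded after the patient knows the arm

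*SAP*

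**What the plan says.** **Baseline rule.** SAP 3.4: "baseline measurements will be the most recent (i.e., last non-missing) value prior to receiving the first dose of study medication". Protocol 9.8.1 has the same anchor: "baseline measurements must be the most recent value prior to receiving the first dose of study medication". Both allow exceptions, but SAP 8.3.3 (quality of life) makes none.

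**Timing of randomisation.** Table 1 of the protocol places it at Cycle 1 Day 1. Note 6 adds: "Randomization may occur on Day -1. Patients scheduled for Cycle 1 Day 1 on Monday may be randomized on the preceding Friday".

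**Blinding.** Protocol 5.11: "This is an open-label study".

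**Timing of questionnaires.** Note 1 to Table 1: "All assessments must be performed predose and within the visit specified windows, unless otherwise described". Note 15 says the questionnaires "must be performed before the patient is evaluated by the Investigator or designee on the day of the scheduled visit". Protocol 6.6.1 repeats this. None of these refers to randomisation or to disclosure of the arm.

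**Instruments.** Table 1 schedules QLQ-C30, DLQI and GP5 at screening and at Cycle 1 Day 1. EQ-5D-5L first appears at Cycle 1 Day 1. SAP 8.3.3.4: "EQ-VAS is the sixth item of EQ-5D-5L", so EQ-VAS follows that schedule.

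**Use of the baseline.** SAP 8.3.3.4: "The change in EQ-VAS from baseline at specific timepoints (3 and 6 months) will be compared between the two arms". SAP 8.3.3.1 plans the same comparison for QLQ-C30 physical and role function. Neither section names a model.

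**The concern.** Randomisation makes the arms comparable on anything measured before it. A self-reported score taken after the patient has learned the allocation lacks that protection. If being given the new drug rather than the standard one changes mood or expectation, the baseline itself differs between arms because of the allocation. That difference enters the change score with the opposite sign. On scales where a higher score is better, a lift in the ripretinib baseline would make ripretinib's later change look worse. The direction cannot be known from the documents.

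EQ-VAS is the most exposed. It asks about health on the day of completion, and the supplied schedule has no earlier EQ-VAS to fall back on. At stake is the interpretation of three between-arm comparisons (physical function, role function, EQ-VAS), each at two timepoints.

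**Working it through.** The plan gives no sample size, power or alpha for the quality-of-life comparisons, so there is no stated figure to reproduce.

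**1. The gap.** Day -1 to Day 1 is 1 day, and Friday to Monday is 3 calendar days. With same-day randomisation the gap is 0 days, but the order of questionnaire and randomisation is still not fixed.

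**2. Which score becomes the baseline** (Table 1 schedule combined with SAP 3.4):

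| Instrument | Screening | Cycle 1 Day 1 | Score selected | Arms compared on change? |
|---|---|---|---|---|
| QLQ-C30 | yes | yes | Cycle 1 Day 1 | physical and role function, 3 and 6 months |
| EQ-VAS | no | yes | Cycle 1 Day 1 (the only one) | yes, 3 and 6 months |
| DLQI | yes | yes | Cycle 1 Day 1 | no, descriptive only |
| GP5 | yes | yes | Cycle 1 Day 1 | no, descriptive only |

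**3. Size of the bias.** Let p be the share of patients whose baseline is recorded after they know the arm, taken as equal in both arms. It includes same-day patients randomised before the questionnaires. Let d be the ripretinib-minus-sunitinib difference in baseline that this knowledge causes among them. If later scores are unaffected by the baseline shift:

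bias in the between-arm difference in change = −p × d

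Neither quantity is in the documents. On assumed values, for a 0–100 scale (SAP 8.3.3.1 gives this range for QLQ-C30; it is assumed for EQ-VAS), the absolute bias in points is:

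| | d = 0 | d = 3 | d = 10 |
|---|---|---|---|
| p = 0 | 0 | 0 | 0 |
| p = 0.25 | 0 | 0.25 × 3 = 0.75 | 0.25 × 10 = 2.5 |
| p = 1 | 0 | 3 | 10 |

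The bottom-right cell is the product of two assumed maxima. Adjusting for the affected baseline with an assumed slope of 0.5 would halve each entry without removing it.

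**4. What a small net shift would do to a test.** Assume no true effect, a simple comparison of change scores, two-sided alpha 0.05 and SE = SD × √(2/n). With n = 213 per arm and SD = 15, SE = 15 × √(2/213) = 1.45. A net shift of 2 points is then 2/1.45 = 1.38 standard errors. Rejection rates for an assumed SD of change of 15 to 25:

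| Net shift p × d | 213 per arm | 150 per arm |
|---|---|---|
| 0 | 0.05 | 0.05 |
| 1 | 0.07 to 0.11 | 0.06 to 0.09 |
| 2 | 0.13 to 0.28 | 0.11 to 0.21 |
| 3 | 0.24 to 0.54 | 0.18 to 0.41 |

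Only the 213 comes from the documents, and it ignores attrition by 3 and 6 months. The 150, the SDs and the shifts are assumptions. With a baseline taken before randomisation, p = 0 and the rate returns to 0.05.

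**The case against.** - **The problem may be negligible.** Randomisation at Cycle 1 Day 1 is the default and note 6 only permits an earlier date. No section says when patients are told the arm, and drug is first dispensed on Day 1. This stands: knowledge of the arm at baseline is an inference from the open-label design, and p and d can both be close to zero. A reader might infer from the table above that a bias of several points is expected. The documents do not support that.
- **The recall period protects QLQ-C30.** Protocol 6.10.3.1 describes its items as covering the last week. With a gap of at most 3 days, at least 4 of the 7 days precede randomisation. This lessens the concern for QLQ-C30, although the answers are still given afterwards. It does not help EQ-VAS.
- **Follow-up is open-label too.** The 3- and 6-month scores come from patients who know their arm, and no choice of baseline changes that. True, but the baseline component is a separate error and can be avoided.
- **The screening score is a poor substitute.** It can be up to 28 days old. Imatinib need only have stopped 10 days before the first dose, and earlier toxicities need only have resolved within the week before it. The score may therefore describe a different clinical state. This stands, and it is why the main baseline should not move to screening.
- **Version.** The SAP is based on protocol Amendment 6 and lists EQ-VAS among other secondary objectives, whereas the supplied protocol lists EQ-5D-5L as exploratory. The schedule could be checked only in the supplied protocol.

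**Conclusion.** The gap is real but modest. As written, baseline physical function, role function and EQ-VAS may be recorded after the patient knows the arm, and nothing prevents this even with same-day randomisation. EQ-VAS is the most vulnerable. The bias in the between-arm change is p × d in absolute size. Neither factor is given, the direction is unknown, and the value can be near zero.

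Three stronger readings are not supported:

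- **That the trial's main conclusions are at risk.** These endpoints lie outside the hierarchical sequence in SAP 8.5, so PFS, ORR, OS and familywise error are unaffected.
- **That all four instruments give biased comparisons.** SAP 8.3.3.2 and 8.3.3.3 only summarise DLQI and GP5 descriptively.
- **That patients are known to be aware of their arm at baseline.** The documents show only that they may be.

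The point is worth acting on because the remedy is specific and costs almost nothing.

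**What to change.** 1. **Protocol Table 1, notes 6 and 15.** Require the baseline questionnaires, EQ-5D-5L included, to be completed before the IRT randomisation call, whether that call is on Day 1, Day -1 or the preceding Friday. State in SAP 8.3.3 that this set is the quality-of-life baseline. Otherwise a repeat on Day 1 would displace it under the last-value rule in SAP 3.4.
2. **SAP 8.3.3.** Report by arm how many baseline scores followed randomisation. Add two sensitivity analyses of the 3- and 6-month comparisons: one using the screening QLQ-C30 score for those patients, and one restricting EQ-VAS to patients whose baseline preceded randomisation. Membership of that EQ-VAS subset is settled before allocation, so the arms remain comparable within it.

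Keep the main baseline as it is for everyone else and do not replace it with the screening score.

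The cost is a small change in visit order and a little extra analysis, and the EQ-VAS sensitivity analysis uses fewer patients. Item 2 assumes that ePRO completion and IRT randomisation times are both available. If enrolment has closed, only item 2 can still be done.
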